The principal action of ACE inhibition is a disruption of the conversion of Ang I to Ang II and consequently, inhibition of the Ang II effects such as vasoconstriction. Angiotensin converting enzyme inhibition may trigger additional events as a result of protection of other peptides. Inhibition of ACE also prevents degradation of kinins into inactive peptides. Kinins act as endogenous vasodilators via stimulation of nitric oxide and release vasodilatory prostaglandins; thus kinins contribute to renal vasodilatory actions of ACE inhibitors, particularly in the medullary circulation. Indeed, blockade of ACE or deletion of kidney ACE reduces the severity of the hypertension that develops with chronic Ang II or Ang I infusions showing that ACE mediated de novo formation of Ang II is an essential step in the full development of hypertension. Ang II receptor blockers (ARB) are a specific class of antagonists that block AT₁ receptors at the tissue level. Angiotensin II, generated by non-ACE mechanisms, could be blocked at the receptor level by an ARB. However, increases in Ang II concentration after ARB therapy may stimulate AT₂ receptors if receptors are not fully blocked.

The use of ARBs and ACE inhibitors has become common practice in treating patients with diabetes. Because RAS activation plays such a central role in the development and progression of DN, there has been extensive interest in the potential hope for reduction in morbidity and mortality by using agents that block 1 or other ore steps in the RAS. Accordingly, the assessment of urinary AGT as an early biomarker of the status of the intrarenal RAS may be of substantial importance. It may be particularly helpful in serving as a means to determine efficacy of the treatment to reduce intrarenal angiotensin II levels.

In our experience urinary AGT remains elevated in patients treated with ACEI or ARBs and present a novel treatment target (with an easily measurable biomarker)

Hypothesis 2: SGLT2 inhibition will reduce urinary AGT in subjects with 2 diabetes, and this reduction will correlate with reduction in BP.

Rationale:

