Immortalized mouse proximal tubule cells consists of cells originating from the early segment of the mouse proximal tubule. To demonstrate the effects of high glucose on AGT expression in this cell line, mPTCs were seeded on 6-well plates at a density of 5.0×105 cells per well. Before treatment in high glucose, the cells were rinsed with PBS and treated in 1.5 mL serum-free DMEM (5 mM glucose) for 8 hours. For high glucose treatment, serum-free Dulbecco Modified Eagle's Medium (DMEM) was supplemented with glucose to a final concentration of 5 mM (control), 15 mM, or 25 mM (n = 4). The cells were incubated at 37 °C for 24 hours. After treatment, cell lysates were prepared. AGT protein was detected via western blot analysis. The results of this experiment showed that our mPTC cell line exhibits a significant increase in AGT expression under high glucose conditions (15 mM and 25 mM glucose) compared to normal glucose (5 mM glucose). To test the effects of high glucose on AGT mRNA, cells were cultured as previously described in serum-free DMEM with 5 mM or 25 mM glucose (n = 3) and incubated at 37 °C.

After 24 hours, AGT mRNA was quantified via qRT-PCR. AGT mRNA relative to GAPDH mRNA was found to be significantly higher after treatment in 25 mM glucose.

The results of these preliminary experiments demonstrate that our mPTC line exhibits very low expression of AGT under normal glucose conditions (5 mM).

The impact of treatment with an SGLT2 inhibitor on intra –renal AGT production is unknown. Additionally, it is unclear what the impact of having significant glycosuria will have on AGT production. Finally, it is important to determine if there are differential effects on AGT production between SGLT2 inhibition and other methods of improving glycemic control, such as Sulfonylurea therapy

Proposed Studies

We propose to conduct a single-center randomized, double blind, cross over study of the effect of Dapagliflozin over 6 weeks, followed by placebo over 6 weeks on the other treatment allocation (those getting placebo first will cross over to Dapagliflozin and vice versa). Treatment will be stratified according to the underlying presence or absence of hypertension.

- 1. Type 2 diabetes with hypertension and on RAAS blocking drugs with stable blood pressure on therapy for at least 30 days; n= 20
- 2. Type 2 diabetes without hypertension and not on RAAS blocking drugs n=10

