If we are unable to recruit 10 patients without hypertension we will increase the number with hypertension for a total of 30. Stratification by hypertension status will remain and is important in understanding the effect of SGLT2 inhibition in patients not on BP lowering drugs

In addition a Sulfonlyurea (SU) arm will also be included -10 patients who are on metformin and other background therapy (with the exclusion of SGLT-2 inhibitor and sulfonylurea) will be recruited. This will be an open-labeled arm. Patients will assessed at baseline. They will then receive usual care for 6 weeks. At the end of 6 weeks, patients will then undergo another assessment before being provided SU for 6 weeks. At the end of 6 weeks, patients will undergo assessment again. The aim is to determine whether any effects seen with Dapagliflozin are specific to that drug or related simply to improved glycemic control.

Inclusion criteria;

As per the current approved indications for Dapagliflozin. In addition;

- 1. Type 2 diabetes with hypertension (history of hypertension in clinical records and on medication for management of hypertension) and on RAAS blocking drugs; or
- 2. Type 2 diabetes without hypertension and not on RAAS blocking drugs
- 3. Hemoglobin A1c between 7% 10% inclusive
- 4. Background therapy for diabetes to include maximally tolerated dose of metformin.
- 5. For the dapagliflozin/placebo arm, in addition to metformin, sulfonylureas and/or insulin is allowed
- 6. Estimated glomerular filtration rate (eGFR) > = 60 ml/min
- 7. Between the ages of 18 -75
- 8. Capacity to understand and sign the informed consent.

Exclusion criteria:

- 1. Current use of Dapagliflozin or any SGLT2 inhibitor
- 2. History of intolerability to Dapagliflozin
- 3. Patients with current and past history of bladder cancer
- 4. Patients with unexplainable baseline hematuria
- 5. All current contraindications of Dapagliflozin as per the label
- 6. Severe hepatic insufficiency and/or significant abnormal liver function defined as aspartate aminotransferase (AST) >3x upper limit of normal (ULN) and/or alanine aminotransferase (ALT) >3x ULN
- 7. Total bilirubin >2.0 mg/dL (34.2 μ mol/L)
- 8. Estimated glomerular filtration rate (eGFR): <60 mL/min (calculated by Cockcroft-Gault formula)
- 9. Recent Cardiovascular Events in a patient:
- 10. Acute Coronary Syndrome (ACS) within 2 months prior to enrolment

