The IP and placebo will be labeled identically. The labels will be prepared according to Good Manufacturing Practice (GMP) and local regulatory guidelines. AZ will provide with prefilled bottles of Dapagliflozin 5 mg and the matching placebo. Labelling will be done by the sponsor.

Randomization:

The randomization code will be generated and provided by the sponsor to the site which the research site personnel will follow.

Dose and treatment regimens: After the subject has started the 5 mg dose of Dapagliflozin or the medication in test period 1, the subject will be called 1 week after initiation of study drug. If the subject is tolerating the medication, the dose will be increased to 2 tabs of placebo or 10mg of Dapagliflozin. If for some reason, the subject is not tolerating the medication the subject will continue on 5 mg daily, particularly if dizziness is present. For the sulfonylurea arm, titration of the sulfonylurea and the placebo will be at the principal investigator's discretion as per usual care. For all the patients, titration of the background medications that have the potential of causing hypoglycemia, titration of the background medications will be at the principal investigator's discretion. The purpose of titration will be to prevent hypoglycemia while the patient is in the study.

Discontinuation of IP:

The investigational drug will be discontinued according to the following criteria:

Discontinuation procedures

Patients with a central laboratory ALT and/or AST >3x ULN will be scheduled for a follow-up visit within 3 days following the receipt of the result. Patients will be discontinued from study if the initial and repeat laboratory tests meet any of the following criteria:

1. ALT and/or AST are $>3 \times$ ULN and TB $>2 \times$ ULN

2. ALT and/or AST are >5 x ULN for \ge 14 consecutive days, at any time after initial confirmatory results

3. ALT and /or AST are $> 8 \times ULN$

4. Study drug will be discontinued when eGFR is persistently $<60 \text{ ml/min}/1.73\text{m}^2$. Clinical judgement by the Principal Investigator will be used to determine if the observed decrease in eGFR $< 60 \text{ ml/min}/1.73\text{m}^2$ warrants discontinuation after the eGFR is repeated after the initial decrease in eGFR is noted.

5. Pregnancy confirmed by a positive pregnancy test or otherwise verified

Sample size calculation and statistical analysis:

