This is a pilot study. Data from this study can be used to derive the sample size for an adequately powered study. Exploratory data analysis: All data will be cleaned and logically checked.

Exploratory analysis will be conducted to examine the distributions of each variable by means of plots (bar charts, box plots, and normal probability plots) and goodness-of-fit test statistics. Means and percentages of baseline variables will be compared between the groups. Possible outliers will be detected. Data transformation will be used to normalize the distribution of continuous variables and to improve linearity in the linear regression analyses if needed.

Comparisons of continuous variables between groups will be performed using t-tests. Chi-square tests will be employed for comparisons between categorical data. Linear regression models will be fit to examine the association between a continuous dependent variables and possible independent co-variables. Data analyses will be performed using SAS version 9 (SAS Institute Inc., SAS/STAT User's Guide, Version 9. Cary, NC: SAS Institute Inc. 2007).

Patient Safety:

A copy of the MedWatch/AdEERs report will be faxed to AstraZeneca at the time the event is reported to the FDA. It will be the responsibility of the investigator to compile all necessary information and ensure that the FDA receives a report according to the FDA reporting requirement timelines and to ensure that these reports are also submitted to AstraZeneca at the same time. When reporting to AstraZeneca, a cover page will accompany the MedWatch/AdEERs form indicating the following:

- Investigator Sponsored Study (ISS)
- The investigator IND number assigned by the FDA
- The investigator's name and address
- The trial name/title and AstraZeneca ISS reference number

The collection of AEs should start after the signing of the informed consent. Investigative site will also indicate, either in the SAE report or the cover page, the causality of events in relation to all study medications and if the SAE is related to disease progression, as determined by the principal investigator. The site research personnel will send SAE report and accompanying cover page by way to AstraZeneca: [contact] or fax number is [contact].

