- 11. Visit 9 (the day after visit 8): The subject will return the ABPM.
- 12. Visit 10 (telephone visit): After the subject has started the medication in test period 2, the subject will be called 1 week later. If the subject is tolerating the medication, the dose will be increased to 2 tablets daily (10 mg). If for some reason, the subject is not tolerating the medication the subject will continue on 5 mg daily, particularly if dizziness is present. The patients will also be asked if they have had any low blood sugars and what time the low blood sugars were. The blood sugars will be relayed to the PI in case there is any hypoglycemia. The PI will then make the necessary changes to the patient's background therapy to prevent further hypoglycemia.
- 13. Visit 11 (telephone visit): will be a telephone visit that will occur 2 weeks after visit 10 which is also a telephone visit. The purpose of the telephone visit is to ensure that the subject is tolerating the medication. This is particularly important if the dose had been increased to the maximum dose of 2 tablets (10 mg) during visit 7. The patients will also be asked if they have had any low blood sugars and what time the low blood sugars were. The blood sugars will be relayed to the PI in case there is any hypoglycemia. The PI will then make the necessary changes to the patient's background therapy to prevent further hypoglycemia.
- 14. Visit 12; (end of treatment visit): This visit will conclude test period 2 six weeks after the washout period. During this fasting visit, a brief physical examination will be done, blood and urine samples will be collected, and the EndoPAT procedure will be conducted. Subjects will take the last dose of the second lot of medication on the day of visit 11. Subject will start the 24 hr. AMBP and urine collection after taking the last dose of the medication for test period 2.
- 15. Visit 13: The day after visit 12, the subject will return the AMBP monitor. This concludes the study.

NOTE: In order to give patients flexibility all visit will have a window of +/-7 days for visits **Study Flow chart:**

A: For the study comparing Dapagliflozin and placebo:

Visit 12 (cross over visit- 6 weeks +/- 7 days after visit 8)

- 5- physical examination
- 6- Fasting laboratory work up

(Collection of fasting blood and urine samples)

- 7- Subject is started on ABPM. Subject takes the last dose of the medication given in test period 2
- 8- EndoPAT procedure conducted.

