Visit 13 (the day after visit 12)

Subject returns the ABPM and 24 hour urine collection No physical exam No blood or urine collection

Protocol for the sulfonylurea arm:

Visit 7 (the day after visit 6) Subject returns the ABPM and urine No physical exam No blood or urine collection

Visit 12 (the day after visit 11)

Subject returns the ABPM and 24 hour urine collection No physical exam No blood or urine collection

Measurements:

- 1- Blood pressure will be measured as per clinical practice and we will also do a 24 hr. ambulatory blood pressure monitoring before and after 6 weeks of treatment in the Dapagliflozin/ placebo arm as well as before and 6 weeks after treatment in the Sulfonylurea/placebo arm
- 2- We will also measure vascular compliance/ endothelial function using the EndoPAT test at the same visits as the ABPM only in the Dapagliflozin/placebo arm.
- 3- Spot and 24 hour urine will be collected. Urine samples will be obtained, before and after treatment. After appropriate processing, the samples will be quickly stored at -20°C, and analyzed for concentrations of AGT, albumin, and creatinine within one week of collection as previously described. The urinary AGT concentrations and urinary albumin concentrations will be normalized by urinary creatinine concentrations. Urine creatinine will also be measured and urine AGT/ creatinine calculated to correct the AGT for volume of excretion. Plasma K, renin and AGT will be measured at these visits.
- 4- Fasting plasma glucose will be measured for the Dapagliflozin/placebo and sulfonylurea arm at the following time points: a) at baseline and end of period 1 and b) at baseline and end of period 2.

Blood and urine will be stored at -70°C, for future testing of other biomarkers of renal and cardiovascular disease.

Measurements	Timings
ABPM and 24 hour urine collection	 Dapagliflozin/Placebo arm Before randomization visit (in test period 1) At the end of test period 1 (before entering washout period) At the beginning of test period 2 At the end of test period 2 (at the end of the study)
	Sulfonylurea arm - Before usual care arm visit (ie visit 2 in test period 1)

The table below summarizes the timings of the measurements:

	 At the end of test period 1 At the end of test period 2 (at the end of the study) 		

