Fasting glucose, blood and urine samples	Dapagliflozin/placebo - At the beginning of test period 1 - Before the end of test period 1 - At the beginning of test period 2 - At the beginning of test period 2 - At the beginning of test period 2 Sulfonylurea arm - Before the usual care arm visit (in test period 1)		
	 At the end of test period 1 At the end of test period 2 (at the end of the study) 		
EndoPAT Procedure	 Dapagliflozin/placebo arm only Before randomization visit (in test period 1) At the end of test period 1 At the beginning of test period 2 At the end of test period 2 		

The **primary end point** will be reduction in urine AGT comparing the AGT before and after treatment using a paired ANOVA Test.

Exploratory endpoints will be:

- 1. Examine the relationship between change in plasma K and change in urine AGT
- 2. Examine the relationship between change in BP and change in endothelial function/vascular compliance using the EndoPAT procedure.

Depending on results of this pilot study we will plan further definitive studies of the effect of SGLT2 inhibition on urine AGT, in a study with appropriate statistical power.

Forecasted key milestones dependent on IRB/IEC approval and contracting

1.	Research Agreement executed	Feb 28, 2016
2.	Projected IRB/IEC approval	Feb 28, 2016

- 3. First Subject In Apr 29, 2016
- 4. Last Subject In (100% enrollment) Apr 30, 2017
- 5. Last Subject Last Visit (Treatment end) Jun 30, 2017
- 6. Publication Jan 30, 2018

References

- 1. McFarlane SI. In: Izzo JL, Black HR, eds. *Hypertension primer: The essentials of high blood pressure*. Lippincott Williams & Wilkins; 2003:488.
- 2. National diabetes fact sheet. 2011

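### The primary analysis of urine AGT is stated only as a before/after comparison; no section assigns it the dapagliflozin-versus-placebo contrast that the crossover was built to estimate

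*Combined protocol and SAP*

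**What the plan says.** Proposed Studies sets out a "single-center randomized, double blind, cross over study of the effect of Dapagliflozin over 6 weeks", with placebo in the other six-week period and 30 patients in this part of the trial. The flow chart carries the heading "For the study comparing Dapagliflozin and placebo".

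The primary end point is defined after the table of measurement timings as "reduction in urine AGT comparing the AGT before and after treatment using a paired ANOVA Test". The Measurements section matches it: "Urine samples will be obtained, before and after treatment". Hypothesis 2 names no comparator either: "SGLT2 inhibition will reduce urinary AGT in subjects with 2 diabetes".

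The section on sample size and statistical analysis adds t-tests between groups, chi-square tests and linear regression. It does not say which groups are meant, ties none of these methods to urine AGT, and mentions no treatment, period or patient term. It calls the trial a pilot and gives no alpha, SD or effect size. On later use it says: "Data from this study can be used to derive the sample size for an adequately powered study".

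**The concern.** A placebo crossover exists so that each patient's value on drug can be set against the same patient's value on placebo. A before/after comparison does not do this. It adds to the drug effect whatever else moved AGT over the six weeks, such as time, study participation, regression to the mean or a change in other treatment. Running it separately in each period gives two uncontrolled changes, which is still not an estimate of the difference between them.

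The plan itself leaves room for non-drug change. Its Rationale links glucose to AGT, and background glucose-lowering therapy may be adjusted during the study: "The purpose of titration will be to prevent hypoglycemia while the patient is in the study".

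With no alpha or decision rule stated, the main harm is to the estimate. That estimate is what the pilot passes on to the powered study.

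**Working it through.** **1. The text.** Four places could supply the missing contrast, and none does.
- The primary end point sentence compares before with after and does not say which treatment.
- The t-tests between groups leave the groups undefined. The paragraph just before uses the word for baseline variables. An unpaired t-test would also ignore that each patient receives both treatments.
- The regression sentence is generic.
- The flow-chart heading introduces a list of visits and names no outcome or test.

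**2. What each analysis estimates.** Let Δ be the true reduction due to dapagliflozin and d a non-drug fall that is the same in both periods.
- Change on dapagliflozin = Δ + d
- Change on placebo = d
- Average over both periods = Δ/2 + d
- Dapagliflozin minus placebo = (Δ + d) − d = Δ

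Only the last is free of d.

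**3. Inputs for an illustration.** From the documents: n = 30. Assumed, because the documents give no value: two-sided 0.05, 15 patients per sequence, no carry-over, no dropout, and drift of 0.2, 0.3 or 0.5 in units of the SD of the before/after change. There is no figure in the plan to reproduce.

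**4. No drug effect, test on dapagliflozin alone.** The noncentrality is λ = d√30 on 29 degrees of freedom.

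| Drift d | λ | Rejection, drift in both periods | Rejection, drift in period 1 only |
|---|---|---|---|
| 0.2 | 1.10 | 18.5% | about 8% |
| 0.3 | 1.64 | 35.5% | about 12% |
| 0.5 | 2.74 | 75.4% | about 24% |

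The last column is simulated. Only half the patients take dapagliflozin in period 1, so the average drift is d/2. The crossover contrast with a period term rejects in about 5% of simulated trials throughout. If both periods were pooled into one before/after test, rejection would be 27–32%, 50–61% and 91–96%, for correlations of 0.3 to 0 between a patient's two changes.

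**5. True reduction of 0.5 SD, drift of 0.3 SD in both periods.**
- Drift downward: before/after estimate 0.5 + 0.3 = 0.80.
- Drift upward: 0.5 − 0.3 = 0.20, and power falls from 75% to about 18%.
- Crossover contrast: 0.50 in both cases.
- With drift in period 1 only, the before/after estimates are 0.65 and 0.35.

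A required sample size varies as 1/effect². At a fixed SD, planning on 0.80 would give (0.5/0.8)² = 0.39 of the number needed. Planning on 0.20 would give (0.5/0.2)² = 6.25 times that number.

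**6. Precision of the controlled contrast.** Let ρw be the correlation within a period and ρb the correlation between periods. In the same units:
- SE of the before/after change = √(1/30) = 0.183.
- SE of the end-of-period contrast = √[(1 − ρb)/(1 − ρw)/30].
- SE of the contrast of changes = √(2/30) = 0.258.

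| ρw / ρb | SE, end values | Power at 0.5, end values | Power at 0.5, baseline-adjusted (simulated) |
|---|---|---|---|
| 0.5 / 0.5 | 0.183 | 75% | about 74% |
| 0.7 / 0.5 | 0.236 | 54% | about 60% |
| 0.8 / 0.5 | 0.289 | 39% | about 54% |

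The before/after change has 75% power in all three settings when there is no drift, and the contrast of changes has 46%.

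**7. Period term.** If it is left out, the bias is (n1 − n2)/(n1 + n2) × period difference. With 18 and 12 patients per sequence and a period difference of 0.5 SD, that is 6/30 × 0.5 = 0.10 SD. The documents do not state the allocation ratio, so the term belongs in the model.

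**The case against.** A reader might infer that the plan analyses dapagliflozin alone and leaves the placebo period unused. Hypothesis 2 and the stated purpose of the sulfonylurea arm, to learn whether "any effects seen with Dapagliflozin are specific to that drug", encourage that reading. The documents do not support it. The end point sentence names no drug, and both Proposed Studies and Measurements use the word treatment for placebo as well as dapagliflozin. Urine is scheduled in both periods, and a single before/after difference would not need an ANOVA. A repeated-measures analysis over both periods is at least as plausible. What remains is that the contrast is unstated; the control itself is present.

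Three further objections carry weight.
- The drift values and the alpha are assumed, and the rejection rates in the table apply only to a dapagliflozin-only test. They are not error rates of this trial.
- Background therapy is adjusted to prevent hypoglycaemia. Such changes may be more frequent on active drug, and the placebo contrast would not remove those.
- This is a pilot and placebo data are collected, so the contrast could be recovered at analysis. That lowers the damage, but it leaves the choice of primary contrast until after the data are seen. Pilot status excuses the absence of a power calculation, not of a defined primary estimate.

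**Conclusion.** The concern holds as an unstated primary contrast. The one analysis assigned to urine AGT is before against after, and nothing elsewhere supplies the comparison with placebo. Taken at its word, whether in one period or both, it yields no placebo-controlled estimate.

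The direction and size of any bias cannot be known from the documents. The illustrative figures show that moderate drift could matter with 30 patients, given equal sequences, no carry-over and drift common to both treatments. This should be corrected before analysis. Confidence is high on what the text omits; the documents do not settle what its authors intended.

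**What to change.** **Change.** Rewrite the primary end point sentence to define the estimate as the within-patient dapagliflozin-minus-placebo difference in end-of-period urine AGT/creatinine, on the log scale if skewed, with a 95% CI. Take it from a crossover model with treatment and period as fixed effects and patient as a random effect, or from the equivalent analysis of within-patient period differences. Adjust for the difference between the two period baselines. Keep the before/after changes within each treatment as descriptive. If a repeated-measures ANOVA was intended, write out its terms and this treatment contrast.

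**Specimen.** State whether spot or 24-hour urine is primary. The visit text provides a urine sample at the start and end of both periods. For 24-hour urine, the timings table lists a collection at the start of period 2, but visits 8 and 9 mention none. Reconcile these before using it as a baseline, or use end-of-period values alone.

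**Cost.** No additional patients or visits. The controlled contrast can be less precise than the uncontrolled change, and the period term costs one degree of freedom. Baseline adjustment recovers part of the loss when within-period correlation is high, but relies on the washout having cleared the first treatment. The contrast still includes any background-therapy changes that dapagliflozin itself brings about, so these should be recorded and reported by period.
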